Key informant interviews (KIs): Qualitative key informant interviews (N=35-50 or until thematic saturation is reached) will be conducted with both public and private community-based health providers, NGO workers, community health workers (CHWs), and parents of young women. Interviews will also be conducted with government officials at the community and M Ward levels (wards are the smallest administrative unit of governmental ministries). These interviews will focus on qualitative mapping of adolescent health and treatment-seeking pathways and providers in the study area, and factors in the family, community, and elsewhere that influence adolescent girls' and young women's health. Interviews will also explore the impacts of the pandemic and lockdowns on adolescent girls' and families' health and well-being, and any programs or approaches used to mitigate impacts. We will also explore intentions and motivations of healthcare providers and political leaders concerning the implementation of integrated reproductive, mental, and sexual healthcare to address the impacts of COVID. The KIs will also provide insight into aspects of the intervention and evaluation tools requiring modification. KIs will also be invited to join a community advisory board (CAB) for the duration of the project (see description above).

In-depth interviews with adolescent girls and young women (IDIs): Qualitative in-depth interviews will be conducted with 20-70 or until thematic saturation is reached AGYW (aged 15-25 years old) to understand their experiences with healthcare in the study area, treatment-seeking patterns, and factors in the family, community and elsewhere that influence their health. Interviews will also include a section with questions about young women's experiences during COVID and associated lockdowns. Young women will also be asked to comment on the proposed intervention's feasibility and acceptability, and provide input on aspects of the intervention and evaluation tools that need modification. We will also discuss intervention components with young women, and seek to learn about sources of support/ways of coping during the pandemic that might be incorporated. Roughly equal numbers of married and unmarried young women will be recruited for participation. Young women will be recruited with assistance from the NGO programs conducted by Apnalaya (see description above), CHWs (their involvement will be covered by the Indian IRBs), and referrals from other participants.

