- iv. the methods to uphold confidentiality *Write here*

B What are the conditions or procedures for sharing of materials and/or distributing for future research projects? *Write here*

C Is widespread sharing of materials planned? *Write here*

D When and under what conditions will materials be stripped of all identifiers? *Write here*

E Can donor-subjects withdraw their materials at any time, and/or withdraw the identifiers that connect them to their materials? *Write here*

- i. How will requests to withdraw materials be handled (e.g., material no longer identified: that is, anonymized) or material destroyed)? *Write here*

F Describe the provisions for protection of participant privacy *Write here*

G Describe the methods for the security of storage and sharing of materials *Write here*

6. **Subject Population:** Provide a detailed description of the types of human subjects who will be recruited into this study.

Qualitative data collection will be collected from the following individuals:

Key informant interviews (KII) (N=35-50 or until thematic saturation is reached) will be conducted with both public and private community-based health providers, NGO workers, community health workers (CHWs), and parents of young women. Interviews will also be conducted with government officials at the community and M Ward levels (wards are the smallest administrative unit of governmental ministries). KIIs will also be invited to join a community advisory board (CAB) for the duration of the project.

Adolescent girls and young women (N=20-70 or until thematic saturation is reached) between the ages of 15-25 years old living in the study area. Consent will be obtained from the individual and her mother (if the participant is unmarried and under the age of 18). Participants over the age of 18 are considered adults, and can provide consent for themselves. Participants married and under the age of 18 are considered emancipated minors, and as such, can also provide consent for themselves. Roughly equal numbers of married and unmarried young women will be recruited for participation.

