The participants for the formative qualitative research (both key informants and young women) will be recruited primarily from Apnalaya's (community-based organization partnering on this study) established networks in the community over their 45 year-long work in the study area. As needed, additional recruitment will be from established networks of community leaders, NGO directors and staff, religious leaders, community health workers, and female community mobilizers. These networks have been established through the PI's previous work in the study area. Based on our previous work, we anticipate that these sources will easily yield the numbers of key informants (N=35-50) and adolescent girls and young women (N=20-70) required for the qualitative data collection in the formative stage. Mothers of girls interviewed will be asked to also participate in separate key informant interviews and theater testing groups, facilitating recruitment of this group.

For the quantitative portion of the formative research, a random sample of adolescent girls and young women (AGYW; ages 15-25 years old) seeking care at a set of public (N=3) and private (N=3) healthcare facilities in the study area will be referred by their healthcare provider and/or Apnalaya's health projects and asked to participate in a brief survey using validated measures to discuss their patterns of healthcare-seeking (where they go for different problems, and what influences those choices), and their perceptions and experiences with adolescent healthcare. Twenty to twenty- five AGYW will be surveyed from each facility, with a total N=150. Based on recent estimates of service usage, clinics in the study area see approximately 80-100 young women in the age range of 15-25 years old per month. Thus, we do not anticipate any challenges recruiting the sample size required for this quantitative survey.

Theater-testing group participants will be recruited similarly to the qualitative interviews above, and participants from the surveys may also be invited to join the theater-testing groups.

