ii. If requesting a waiver of **signed** authorization, describe why it would be impracticable to obtain the subject's signed authorization for use/disclosure of this data: *Write here*

The investigator assures that the protected health information for which a Waiver of Authorization has been requested will not be reused or disclosed to any person or entity other than those listed in this application, except as required by law, for authorized oversight of this research study, or as specifically approved for use in another study by an IRB.

Researchers are reminded that unauthorized disclosures of PHI to individuals outside of the Yale HIPAA-Covered entity must be accounted for in the "accounting for disclosures log", by subject name, purpose, date, recipients, and a description of information provided. Logs are to be forwarded to the Deputy HIPAA Privacy Officer.

6. Process of Consent/Accent: Describe the setting and conditions under which consent/assent will be obtained, including parental permission or surrogate permission and the steps taken to ensure subjects' independent decision-making.

Formative phase of the research: Verbal consent for all adult (18 years or older, and under the age of 18 but married and therefore emancipated) participants will be obtained directly from the participant prior to the beginning of any study procedures. All qualitative interviews and the quantitative survey in the first formative research phase of the study will be conducted in a private room, and consent will also be obtained in this private, confidential space. For participants who are minors (unmarried and under the age of 18), verbal consent will first be obtained from a parent or guardian, and verbal assent will be obtained from the participant. The parent/guardian will be asked to step out of the room for the interview/survey, and the participant will again be asked if they assent to participating in the study. The second assent will be done to ensure the subject is independently choosing to participate.

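### Mothers of interviewed girls are to be invited as informants with no step for the daughter's agreement, which can disclose the participation of women who consented alone.

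*Combined protocol and SAP*

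**What the plan says.** Section I, 4 (ADAPT-ITT Assessment Phase, key informant interviews) plans 35–50 interviews, or until saturation, with several groups that include "NGO workers, community health workers (CHWs), and parents of young women". It gives no number for parents and does not link them to the girls interviewed.

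The link is in Section III, 3a (Recruitment Procedures): "Mothers of girls interviewed will be asked to also participate in separate key informant interviews and theater testing groups, facilitating recruitment of this group". The same paragraph says that formative participants of both kinds come mainly through the partner NGO's networks, and then: "As needed, additional recruitment will be from established networks of community leaders, NGO directors and staff, religious leaders", followed by community health workers and female community mobilizers.

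On who consents, Section I, 6 (Subject Population) says:

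- Unmarried minors: "Consent will be obtained from the individual and her mother (if the participant is unmarried and under the age of 18").
- Adults: "Participants over the age of 18 are considered adults, and can provide consent for themselves".
- Married minors: "Participants married and under the age of 18 are considered emancipated minors, and as such, can also provide consent for themselves".

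Section III, 6 (Process of Consent) gives the same division, except that for minors "verbal consent will first be obtained from a parent or guardian, and verbal assent will be obtained from the participant". It places both consent and interview in a private room.

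Two confidentiality measures bear on the point. Section I, 11 (Minimizing Risks) requests a waiver of written consent in order to reduce the risk of a confidentiality breach. Section IV, 1 says that the formative phase collects no names, and that phone or email details are destroyed after the interview and never linked to the responses.

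**The concern.** The invitation to mothers is stated without conditions. Followed literally, it includes the mothers of women who were entitled to take part without any parent knowing. The reason for approaching such a mother is that her daughter was interviewed, so the approach itself can carry that information. The interviews cover health care, treatment-seeking and family influences on health, within a study of sexual and reproductive health, and the background section describes stigma and taboo around these subjects.

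What is at stake is mainly participant protection. Candour is a secondary matter: a participant who expects her mother to be invited next may speak less freely about family influences, which are a listed interview topic. That effect is a reasonable inference, not something the documents show.

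**Working it through.** The plan gives no figure to reproduce and no power or analysis quantity is involved. The check sets the recruitment rule beside the consent rules, group by group, and then counts the participants to whom the gap could apply.

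**Step 1. Does inviting the mother disclose anything new?**

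1. *Unmarried, under 18.* A parent or guardian has already agreed, so the family knows. Section I, 6 names the mother as the one who consents, while Section III, 6 accepts any parent or guardian. The invited mother is therefore usually, but not necessarily, the person who agreed. There is little or no new disclosure.
2. *Married, any age.* The participant consents alone. Inviting her mother on the ground that she was interviewed would reveal her participation, unless she had agreed to the approach or her mother already knew. The available text provides for neither.
3. *Unmarried adult.* As for group 2.
4. *Parents reached through NGO or community networks, unconnected to an interviewed girl.* No disclosure arises. The plan permits this route for key informants in general.

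**Step 2. Is there a safeguard elsewhere?** The consent section protects the setting of the interview. The risk and minimization sections address sensitive information. Section IV, 1 covers names, contact details and linkage. None of them deals with telling a mother that her daughter took part. Section IV, 1 also leaves unclear how a participant's mother would be identified once names are not taken and contact details are destroyed.

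**Step 3. How many participants could be affected?**

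- Planned in-depth interviews: 20–70, or until saturation (Section I, 4 and 6).
- Planned mix: roughly equal numbers married and unmarried (same sections).
- Married, and so consenting alone: 0.5 × 20 = 10 to 0.5 × 70 = 35.
- Unmarried: the same 10–35. The split between minors and adults is not given. If none are adults, the total consenting alone stays at 10–35. If all are adults, it is 10 + 10 = 20 to 35 + 35 = 70.

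The documents therefore fix the married component at about 10–35 and leave the unmarried adult addition unspecified. They give no number of mothers to be approached, so a number of actual disclosures cannot be derived.

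**The case against.** The strongest reply has four parts.

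*The mothers are an additional route.* Section III, 3a recruits key informants mainly through the partner NGO and asks these mothers to take part as well. This stands. The route is the only one specific to parents, but it is not exclusive. A reader might infer that parent informants are limited to families that already said yes, and so that Aim 1 will understate parental barriers. The documents do not support this. Parents can be reached in other ways, mothers of self-consenting women were never filtered by permission, and family factors are also sought from the girls, health workers, NGO staff and providers. For the same reason there is no case for re-approaching parents who refused, which would raise its own questions about voluntariness and the tracking of refusers.

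*The word used is girls, which may mean only the younger participants.* For the health clubs, the same section involves mothers only for unmarried minors. This reading is possible, but the sentence on interviews carries no such limit. If it is the intended meaning, it should be stated.

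*Consent materials are not in the file reviewed.* The information sheets may tell participants about contact with mothers or ask their agreement. This is a fair limit on the finding. It does not change the recruitment rule, which as written has no condition.

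*Protections exist, and the harm is inferred.* Interviews are private and separate, and responses are not linked to contact details. The listed risk concerns sensitive information, not the fact of taking part. Violence is not among the topics listed for these interviews, so a reader should not assume that it is. These protections cover what a participant says, but not whether her mother learns that she took part.

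**Conclusion.** The point holds as a gap in participant protection. Section III, 3a sets an unconditional rule for approaching mothers, the consent sections let adult and married participants decide alone, and no available text joins the two with a step for the daughter's agreement. About 10–35 married interviewees, plus an unstated number of unmarried adults, are potentially affected. A reader might take that range as the number whose participation will be revealed. It is not: it counts women who consent alone, and not every mother need be approached or be unaware.

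The conclusion assumes that girls means all interviewees, that roughly equal means about half, and that the consent materials do not already contain this step. Sample size, power, randomization and the quantitative analysis are unaffected.

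**What to change.** Amend the sentence on mothers in Section III, 3a to say, in substance:

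*A participant's mother will be approached for a key informant interview or a theater-testing group only if the participant agrees to this in private after her own interview. Other parents will be recruited through the NGO and community networks named in this section.*

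One rule for all participants is simplest, and it also covers the minor whose consenting parent or guardian was not her mother. Asking at the end of the interview fits Section IV, 1, because the question is put before contact details are destroyed. If the information sheets already contain such a step, a cross-reference in Section III, 3a is enough.

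The cost is a short wording change and slightly slower recruitment of mothers. No extra participants or staff are needed, and parent interviews stay within the planned 35–50.

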An ecological model of youth-friendly service use posits that individual, interpersonal, community, and structural factors all impact provision and uptake.⁽³⁰⁾ The proposed integrated intervention seeks to influence individual, interpersonal, and community levels of the system (Figure 1).

The Study Area

The study community is a low-income, officially-designated "slum" area in northeastern Mumbai with a diverse Hindu, Muslim, and Buddhist population of ≈700,000. Most are long-term migrants from rural areas of Maharashtra and both northern and southern states. Among

[figure not shown]

Figure 1: Ecological model of AGYW SRHR and the pilot intervention.

neighborhood homes, 90% are one-room with a mean family size of 6.2 persons. Construction materials are varied with some houses of durable materials and many more that consist partially or primarily of found

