materials such as tarps and pieces of wood or tin. Most men are engaged in daily low-wage work, with considerable unemployment. Only 28% of women work for cash income, typically sorting and recycling in a local dumping ground or selling embroidery work. The average monthly family income is INR 5900 (approximately US \$100/month). The population is young; 60.6% are under the age of 25. Among married women, 38% were married before the legal age of 18 years old, and only 5.5% of young women have studied beyond the 10th standard.⁽¹⁰³⁾ The Urban Health Center (UHC) in the study community is a government-funded primary care facility implemented with the Department of Preventive and Social Medicine at T.N. Medical College. The UHC, along with three smaller clinics (known as health posts), constitute the primary government healthcare for the study area. CHWs work out of the health posts and make door-to-door rounds to provide education and distribute basic interventions and medications. My mentors and I have partnered with the UHC in previous projects.^(66, 104, 105) The UHC is developing an adolescent-friendly health clinic, and being expanded. Healthcare is also provided through privately-funded NGO clinics, and a wide variety of private practitioners, primarily non-allopathic (e.g., *ayurvedic*, *unani*, and homeopathic), with about 10% allopathic providers. The private sector has collaborated with ICRW and myself in the past, vital prior relationships that will facilitate the present K01 study. Fieldwork conducted in 2014 found relatively fewer AGYW using private providers as most private sector providers are male. However, my recent discussions and observations suggest that more private providers are expanding their practices to include female nurses and medical assistants, suggesting that more AGYW may begin seeking care in this sector. Seven NGOs work in the community, and one will collaborate with this project. *Apnalaya*, working in the area since 1975, has extensive experience in providing health and social services as well as citizenship and life skills training to youth in the study community. I have previously collaborated with *Apnalaya*. In this project, *Apnalaya* will be involved in two ways. First, as a key NGO working with youth in the study area, one to two members of their team will be interviewed in the key informant interviews in the assessment/formative research phase, and invited to join the community advisory board (function of board described below). Second, they will provide support in recruitment of adolescent girls in the assessment/formative research phase. They routinely hold events with AGYW and provide some health and social services to community members. They will verbally announce/advertise the study to AGYW, and refer interested AGYW to our team for further information and enrollment. Their participation will be covered by the Tata Institute and Indian Council for Medical Research IRBs.

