Adolescent Health Club Component and Evaluation: Households with AGYW ages 15 to 25 will be identified by community health workers from randomly selected block sectors of the study area. Clubs will be conducted in separate neighborhood sectors, to limit contamination. Conducting club meetings near to the lanes adolescent girls live in will make it easier for them to attend. To further assess and address potential contamination, we will ask individuals to verify the adolescent health club they attended in the post-intervention survey, whether they attended an additional health club outside our intervention (such as, in school). If any contamination is evident based on this question, then we will model it. AGYW and their mothers (if unmarried and under the age of 18) will be approached by a member of the research team and the adolescent health club intervention will be explained. If consent is obtained, the AGYW will be enrolled, and randomized to either participate or join the wait-list. AGYW will complete the pre-intervention evaluation instrument upon enrollment. In addition to the activities in the "It's All One" Curriculum spread over eight modules, providers from the sensitization component will attend one meeting to discuss services available in the adolescent-friendly clinics, and hear young women's previous experiences accessing care. Similar to the process for the provider sensitization component, the facilitator will complete a log after each session to code activities as implemented fully, implemented partially or modified significantly and describe any changes. The log will also include a section to document any unusual events associated with any of the sessions, and the effect of these events on implementation, acceptability, or feasibility. Every other session will be observed and documented in fieldnotes that will be analyzed to contribute to process evaluation (see analysis details below). As with the provider component, the log and fieldnotes will enable a qualitative assessment of intervention fidelity. When young women complete the curriculum, they will also complete the post-intervention evaluation instrument. A sub-sample of young women (N=15) will be asked to participate in a focus group discussion to reflect on the club's impact and acceptability. Domains measured by previously validated instruments^(32, 48, 66, 123-126) to be covered in the pre- and post-intervention surveys are shown in Table 3. There are relatively few validated quantitative measures of implementation outcomes,^(127, 128) and none in Hindi, thus the measure we have chosen⁽¹²⁹⁾ will have to be translated and back-translated to ensure comprehension.

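### The only contamination check records club attendance, so club content passed on informally to women still waiting or not yet enrolled is not measured and cannot trigger the promised modelling

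*Combined protocol and SAP*

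**What the plan says.** All of the provisions on contamination are in Section I, item 4, under Adolescent Health Club Component and Evaluation.

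- **Prevention.** "Clubs will be conducted in separate neighborhood sectors, to limit contamination". Meetings are held close to where members live.
- **Check.** "we will ask individuals to verify the adolescent health club they attended in the post-intervention survey", together with a question on attendance at a club outside the study.
- **Use in analysis.** "If any contamination is evident based on this question, then we will model it". No model is specified.
- **Timing.** The pre-intervention survey is taken at enrolment. "When young women complete the curriculum, they will also complete the post-intervention evaluation instrument". The text describes no survey at the end of the wait, and Table 1 lists no survey domain on exposure through other people.
- **Allocation.** After consent, "the AGYW will be enrolled, and randomized to either participate or join the wait-list". Section III, item 3, parts a and b, describe the same enrolment step without mentioning randomisation.

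Section III, item 3a, recruits groups 1 and 2 together. It then recruits a further wait-list group of 25 each time a club finishes, until four groups have been through the curriculum. The quantitative analysis paragraph compares treated group 1 with untreated group 2, treated group 2 with untreated group 3, and treated group 3 with untreated group 4.

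**The concern.** Both check items ask where a woman went. Neither asks what reached her. A woman who learned club content from a member, without attending anything herself, would truthfully report no extra attendance. The modelling step depends on that answer, so it would not start, and the comparison would be reported as uncontaminated.

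Spill-over is plausible in this setting. The Study Area section says that, among "neighborhood homes, 90% are one-room with a mean family size of 6.2 persons". The Pilot Intervention Model section says the intervention aims to act at interpersonal and community levels as well as on individuals, so some spread is part of the intended effect.

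The preventive step is also not firmly tied down. Separate sectors protect the wait-list only if the waiting women live in a different sector from the running club. Randomising individual women, with no rule for those who share a home, does not ensure that.

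What is at stake is the size of the between-group contrast, and of the pre/post gain in the later groups. Both shrink if untreated scores have already been raised by earlier clubs.

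**Working it through.** **1. The plan's own figure.** Inputs from Intervention Power Calculation and Sample Size Considerations: difference 1.3, SD 3, power 85%. No alpha is given, so 0.05 two-sided is assumed.

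- Paired: (3 × (1.960 + 1.036) / 1.3)² = 47.8, so 48 pairs. With the t distribution it is 49.8, so 50 pairs. The stated 50 pairs reproduces.
- Two independent arms, the design the text names: 2 × 47.8 = 95.6, so 96 per arm. The stated figure does not reproduce this way. That is a separate matter and is not pursued here.

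Neither calculation allows for spill-over. The values 1.3 and 3 are used below only as a scale.

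**2. What the check would record.**

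| Exposure before a woman's own club | Recorded? |
|---|---|
| Attended another study club | Yes, in retrospect |
| Attended a club outside the study | Yes, in retrospect |
| Told about content by a relative, friend or neighbour | No |
| Shown club materials | No |

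A wait-listed woman who never completes her own club may not be asked at all.

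**3. Where spill-over would enter the results.** One club lasts about 2.5 months, with 25 women planned per group.

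| Group | Clubs finished at enrolment | Untreated score compared with | Effect of spill-over |
|---|---|---|---|
| 1 | 0 | not used | none |
| 2 | 0 | treated group 1 | enrolment score is clean; exposure during the wait falls inside its pre/post change |
| 3 | 1 (25 women) | treated group 2 | exposure before enrolment raises the untreated score; later exposure falls inside the pre/post change |
| 4 | 2 (50 women) | treated group 3 | as group 3 |

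Two of the three contrasts, and the pre/post gain in two of the four groups, can therefore be diluted. The group 1 versus group 2 contrast cannot be, on the surveys the text describes.

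**4. Size, as a sensitivity range only.** Let c be the share of the effect already gained, equal to the proportion exposed × the share of content gained. The documents give neither, so all values of c are assumptions. For example, 20%, 40% and 60% exposed, each gaining half, give c = 0.10, 0.20 and 0.30.

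- Affected contrast = 1.3 × (1 − c).
- Equally weighted mean of the three contrasts = 1.3 × (1 − 2c/3). The mixed model would weight them differently.
- Sample size multiplier for an affected contrast = 1 / (1 − c)².
- Power of one contrast with 25 per arm = Φ(contrast / (3 × √(2/25)) − 1.96).

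| c | Affected contrast | Mean of three | Multiplier | Power, 25 per arm |
|---|---|---|---|---|
| 0 | 1.30 | 1.30 | 1.00 | 33% |
| 0.10 | 1.17 | 1.21 | 1.23 | 28% |
| 0.20 | 1.04 | 1.13 | 1.56 | 23% |
| 0.30 | 0.91 | 1.04 | 2.04 | 19% |

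The power column treats 3 as the SD of scores in each group and women as independent. A single contrast is weakly powered even with no spill-over, so the column shows relative loss only.

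**The case against.** The strongest reply is that separate sectors already deal with sisters and neighbours, and that the check is a back-up. If whole groups are drawn from different sectors, much of the household and lane route disappears. This stands as far as it goes, but the same paragraph randomises individual women, and the text does not say which description governs. Splitting a household by randomisation can arise only in the first 50 women, since later groups are recruited straight to the wait-list. A sister recruited to a later group is still possible, because no household rule is given.

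Several stronger readings are tempting and are not supported.

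- *Contamination cannot be seen or modelled.* Attendance at another study club or an outside club can be reported in retrospect and modelled. Session logs, fieldnotes and the focus group might mention spread, and enrolment scores of groups 3 and 4 might drift upward, although that would be confounded with calendar time. None of these is planned as a check on spill-over, so the accurate statement is that it is not measured.
- *The protocol's statement on carry-over is wrong.* The Study Design section claims only that some carry-over difficulties are avoided, and it concerns movement within a woman from control to intervention. Spill-over is between women.
- *Every wait-list comparison is diluted.* Group 2's only described untreated score precedes all clubs.
- *Trained community health workers will carry club content.* It is true that "CHWs work out of the health posts and make door-to-door rounds to provide education", but their workshop is provider sensitisation, not the club curriculum, and their rounds are not described as differing between groups. A worker may support some club sessions, which leaves a possible route and no more.

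Figure 2 was not available for this review and might show further survey points. The text describes none.

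**Conclusion.** The point holds in a limited form. The planned check covers attendance only, and the modelling commitment depends on it, so informal spill-over would pass as no contamination. The exposure that matters most is in groups 3 and 4, which supply the untreated scores for two of the three between-group comparisons. For group 2, and for anything groups 3 and 4 learn after enrolling, spill-over is counted within the pre/post change.

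The size is unknown. The range of 1.17 to 0.91 for an affected contrast rests on assumed spill-over of 10% to 30% and on borrowing 1.3, a pre/post difference from another study, as the between-group effect. The conclusion also assumes that untreated scores come from the enrolment survey, as the text implies.

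Since this is a pilot meant to inform a later trial, the gap calls for an inexpensive improvement. It does not invalidate the design.

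**What to change.** 1. **Add two items**: whether a relative, friend or neighbour attended a study club, and whether the woman was told or shown club content before her own club began. Put them in the enrolment survey, where they are informative for groups 3 and 4. Put them, asked retrospectively, in every post-intervention survey to cover the wait, including group 2's. Enrolment items alone would miss group 2, because no club has run when it enrols.

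2. **Use the answers with attendance** in the promised contamination model, specified in advance as a sensitivity analysis. It should not replace the primary comparison: exposure is self-reported, and women who know members may differ from those who do not.

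3. **Place all eligible women in one household in the same group**, across recruitment rounds as well as within the first 50.

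4. **Reconcile the allocation text.** Section I, item 4, and Section III, items 3a and 3b, should agree on whether women are randomised and whether the unit is the woman, the household or the sector.

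The cost is two short questions, a household rule and a wording change. Retrospective answers carry recall error, made worse because the woman has by then learned the content herself, and women who do not finish their club would still be missed at that point. Keeping households together loses a little precision. A survey at the end of the wait would measure exposure more directly but would add a data collection round, so it is not needed for this fix.
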